5 POWER ESTIMATION

The power analyses presented here are based on trial simulation of the primary DIAN multivariate cognitive endpoint (DIAN-MCE) and the use of the multivariate disease progression model (MDPM).

The primary analysis is a single hypothesis test using the MDPM with four clinical/cognitive tests being modeled simultaneously (vs. the previous primary analysis using univariate DPM models of the DIAN Cognitive Composite).

Power Estimation using the MDPM

The power estimate for each scenario is presented in [Appendix VI](#). MDPM with dynamic borrowing of the eligible DIAN-OBS subjects (see [Section 7.2](#) for more details about these eligible subjects and [Section 12.1.4](#) for more details about the dynamic borrowing) led to approximately 95.9% power for a 30% effect size.

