8.2 Type I Error Rate Control

The primary analysis for each study drug is based on a Bayesian posterior probability. This posterior probability of slowing the rate of cognitive decline is used to determine success on the primary efficacy analysis. The posterior probability threshold is selected to control the type I error rate for the multivariate analysis of DIAN-MCE. The type I error rate is the probability of rejecting the null hypothesis that there is no difference in cognitive decline or there is faster decline in the subjects in the active drug arm compared to those in the pooled control group with dynamic borrowing when the null hypothesis is true.

Although this study investigates multiple study drugs with shared placebos for the primary efficacy analysis, no adjustment for multiple drugs will be done. Each drug is considered to have its individual 2.5% type I error rate.

There will be no comparison between study drug arms.

For any secondary analyses based on the MDPM or UDPM, the test will be one-sided with a type I error rate of 0.025 for each analysis. For any secondary analyses based on the linear mixed effects (LME) model or the mixed-effects model for repeated measures (MMRM) or any other frequentist models, the test will be two-sided with a type I error rate of 0.05 for each analysis.

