12.1.5 Thresholds for the Primary Analysis

The procedure for finding the appropriate thresholds for success on the primary analysis are as follows:

1. Simulations were conducted on each of the design scenarios defined in [Appendix VI](#) assuming that the null hypothesis is true for each treatment arm in the DIAN-TU-001 study.
2. The single threshold to the posterior probability is selected in order to maintain at most a one-sided 2.5% type I error rate in all null hypothesis scenarios.
3. If the threshold obtained in #2 is smaller than 0.975, then 0.975 is used. As a result, the simulated type I error rate will be less than 0.025 for all design scenarios.
4. The details are presented in Appendix VI. The threshold of probability of superiority determined by the simulation is 0.981. This threshold will be utilized in all the primary/secondary/sensitivity analyses for determination of statistical significance wherever the MDPM is used.

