12.1.6.5 Sensitivity analyses to evaluate the different administration schedules in ISLT and MMSE

The following analyses will be conducted for the combined population of the mITT population and the eligible DIAN-OBS subjects.

The ISLT was administered to DIAN-OBS subjects only from 2017. Hence, Eligible DIAN-OBS completed fewer ISLT tests in comparison to the other three tests included in the DIAN-MCE. To evaluate the effect of the lack of ISLT assessments in DIAN-OBS, the MDPM will be applied to the DIAN-MCE with only 3 tests: MEMUNITS, WAIS, and MMSE. The MDPM and all its other parameters will be set up similarly to those in [Section 12.1.3](#).

Of the four tests in DIAN-MCE, MMSE is administered annually whereas the other three are administered semi-annually in DIAN-TU-001. To evaluate the effect of this discrepancy, the MDPM will be applied to the DIAN-MCE using only data at the visits where MMSE is administered if the data come from DIAN-TU-001 and all the data regardless of the availability of MMSE if the data come from the eligible DIAN-OBS subjects (all available MMSE, WAIS, MEMUNITS, and ISLT). The MDPM and all its other parameters will be set up similarly to those in [SAP Section 12.1.3](#).

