where, $[x]$ is the floor function (the largest integer less than x). The mean rate of decline as a function of EYO, for a variable v parameter vector $\alpha_v = (\alpha_{v,-15}, \alpha_{v,-14}, \dots, \alpha_{v,15})$ for each variable v is modeled independently as a monotonic Gaussian process:

$$\alpha_{v,k} \sim N^-(\alpha_{v, k-1}, 1.5^2) \text{ for } k = -14, \dots, 15,$$

where the distribution $N^-(m, s^2)$ refers to the negative portion of a normal distribution with mean m and standard deviation s .

The parameter $\exp(\theta)$, represents the cognitive progression ratio, CPR. The parameter is the common rate of slowing across the four endpoints, for a treatment arm. The value of the CPR is interpreted as the ratio of the rate of decline under a treatment regimen compared to the reference group – much like a hazard ratio in a time-to-event analysis. For example, if the CPR is 0.60, then the rate of decline of cognition is slowed by 40% for the regimen compared to the reference group. In the disease progression model, we place a prior distribution on the treatment effect parameter. This prior for θ is centered on no effect ($\theta = 0$) with a standard deviation of 1 for each of the active drug arms. A 1 standard deviation change on the log-CPR scale is equivalent to a CPR change from 1 to 0.37 or from 1 to 2.71, thus this prior is weak, but allows some centering on “no effect”. The primary analysis of this trial is testing the hypothesis that the CPR is less than 1.

$$H_0: \text{CPR} \geq 1$$

$$H_1: \text{CPR} < 1$$

The primary analysis is based on the posterior probability that the CPR is less than 1. If the posterior probability that the CPR is less than 1 is greater than the pre-determined threshold then the primary analysis of slowing the rate of cognitive progression will be accepted. The posterior mean, median, 50%, 75%, 95%, and 99% equal-tailed credible intervals will be presented. The

determination of the threshold of superiority is specified in [Appendix VII](#).

Note: The model can be fitted for any subset of observations at a visit, even if not all four endpoints have been observed. Per protocol, the first three endpoints were collected semi-annually, while MMSE is collected annually. The model is fitted at each of the visits where at least one endpoint has been collected.

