20 APPENDIX VI. DETAILS OF CLINICAL TRIAL SIMULATIONS FOR DIAN-MCE

In order to characterize and understand the performance of the primary DIAN-MCE analysis, we carried out detailed simulations of the design under multiple scenarios as described in this section. The trial is simulated as described, including the accrual and randomization of subjects, pooling of placebos, inclusion of simulated DIAN-OBS data, drop-out rates of subjects and the timing of the analysis as detailed here. A variety of scenarios are simulated with the operating characteristics summarized. The base case scenario presents the best estimates for each of the parameters used to simulate the trial and subjects. The remaining 7 scenarios explore the sensitivity of the design to different possible truths. The assumptions made in this section are based on an analysis of the DIAN-OBS cohort (Data Freeze 11). This section provides an estimate of the power and type I error rate for each study drug.

In particular, we make the following assumptions for our base simulations:

- **Regimen Size:** 70 mutation positive subjects with 3:1 randomization (active to placebo) per arm (53:17 per arm, for 53:53:34 for each arm and the pooled placebo)
- **Distribution of EYO at enrollment:** Uniform between -15 and +10 EYO with a simulation of CDR-global as a function of EYO for trial inclusion ($CDR \leq 1$)

Modeling Cognitive Endpoint Progression: The assumed model for simulating subjects is assumed for simulating virtual subject data. Let \tilde{Y}_{ij} be the 4-dimensional vector of outcomes for subject i , at their j th visit. Let E_{ij} be the estimated years to symptom onset for subject i at visit j .

The distribution for each observation is assumed to be normally distributed:

$$\tilde{Y}_{ij} \sim N_4(\tilde{\mu}_{ij}, \Sigma).$$

The mean for variable v is modeled as

$$\mu_{ijv} = \gamma_{iv} + f(E_{i0} - \delta_i | \alpha_v) + \exp(\theta_{T_i}) [f(E_{ij} - \delta_i | \alpha_v) - f(E_{i0} - \delta_i | \alpha_v)]$$

where the random effect for variable v is simulated as

$$\gamma_{iv} \sim N(0, 1^2) \quad v=1, 2, 3, 4.$$

The random effect for EYO adjustment is simulated as

$$\delta_i \sim N(0, 2^2).$$

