The variance-covariance matrix, Σ , is assumed to (estimated from the DIAN-OBS data) have standard deviations of 0.329, 3.431, 0.280, 0.290 for MEMUNITS, MMSE, WAIS, ISLT, respectively. The pairwise correlations are 0.091 (MEMUNITS and MMSE), 0.136 (MEMUNITS and WAIS), 0.089 (MEMUNITS and ISLT), 0.419 (MMSE and WAIS), -0.088 (MMSE and ISLT), and -0.070 (WAIS and ISLT).

The mean function for each component is

$$f(x) = \begin{cases} 0 & x \leq -15 \\ (1 + [x] - x)\alpha_{[x]} + (x - [x])\alpha_{[x]+1} & -15 < x \leq 15. \\ \alpha_{15} & x > 15 \end{cases}$$

The assumed mean changes as a function of the EYO values for the observational data are presented in Table 13.

Table 13: The Mean for Each Endpoint

α_{EYO}	MEMUNITS	MMSE	WAIS	ISLT
α_{-15}	0	0	0	0
α_{-14}	-0.111	-0.118	-0.093	-0.116
α_{-13}	-0.224	-0.238	-0.192	-0.235
α_{-12}	-0.341	-0.360	-0.297	-0.351
α_{-11}	-0.462	-0.481	-0.404	-0.457
α_{-10}	-0.585	-0.605	-0.513	-0.555
α_{-9}	-0.706	-0.730	-0.622	-0.647
α_{-8}	-0.824	-0.860	-0.736	-0.738
α_{-7}	-0.941	-0.993	-0.853	-0.831
α_{-6}	-1.054	-1.134	-0.974	-0.928
α_{-5}	-1.166	-1.284	-1.100	-1.030

α_{EYO}	MEMUNITS	MMSE	WAIS	ISLT
α_{-4}	-1.276	-1.445	-1.234	-1.134
α_{-3}	-1.388	-1.618	-1.382	-1.242
α_{-2}	-1.511	-1.806	-1.553	-1.351
α_{-1}	-1.653	-2.014	-1.754	-1.458
α_0	-1.817	-2.260	-1.987	-1.558
α_1	-1.990	-2.258	-2.238	-1.646
α_2	-2.161	-3.024	-2.520	-1.724
α_3	-2.336	-3.686	-2.841	-1.792
α_4	-2.536	-4.652	-3.158	-1.856
α_5	-2.750	-6.008	-3.506	-1.919
α_6	-2.950	-7.824	-3.648	-1.990
α_7	-3.123	-9.959	-4.035	-2.077
α_8	-3.272	-12.193	-4.645	-2.189
α_9	-3.436	-14.155	-5.065	-2.325
α_{10}	-3.650	-15.482	-5.314	-2.505
α_{11}	-3.850	-16.500	-5.501	-2.650
α_{12}	-4.050	-17.500	-5.700	-2.800
α_{13}	-4.250	-18.500	-5.900	-2.295
α_{14}	-4.450	-19.500	-6.100	-3.100
α_{15}	-4.650	-20.500	-6.300	-3.250

- **Frequency of cognitive assessments:** Every 12 months
- **Dropout:** 7% annual drop-out rate unrelated to outcome
- **Accrual:** The actual trial accrual is used. The 140 subjects are accrued over 975 days with the 35th, 70th, and 105th being enrolled on days 589, 758, and 918, respectively.
- **CDR-Global:** The trial has an inclusion criterion of a CDR-global of 1 or less. For each subject, a CDR-global is simulated based on their baseline cognitive composite. The simulated cognitive composite is calculated, and a subject is excluded (and replaced) if a CDR-global greater than 1 is simulated.

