4. The post-baseline observations are simulated assuming a treatment CPR value for the respective treatment arm (each scenario/case assumes a value for placebo and each treatment arm). A CPR of 1 corresponds to being identical to the natural history (DIAN-OBS data). The treatment effect is incorporated to the mean for each variable as

$$\mu_{ijv} = \gamma_i + f(EYO_{i0} - \delta_i) + CPR[f(EYO_{ij} - \delta_i) - f(EYO_{i0} - \delta_i)] \text{ for } j = 1, \dots, n_i.$$

A drop-out time is simulated for every subject. This is simulated assuming an exponential time to drop-out matching the assumption of the annual drop-out rate within 52 weeks. At each time of analysis, if the subject has dropped out, then their cognitive values from that point forward are ignored in the analysis.

For the base case, 66 DIAN-OBS subjects are assumed. The follow-up is simulated as uniformly distributed from 3 to 6 years (meaning 3, 4, or 5 years of exposure are equally likely). All other components are simulated as above.

Simulation Scenarios

The following scenarios are simulated. In each scenario, 6 cases are simulated. The cases assume the target treatment arm has a CPR of 1, 0.80, 0.75, 0.70, 0.65, and 0.60. The following scenarios are simulated:

-
- A. Base scenario (described above)
- B. Simulate different distributions of the EYO at entry. One scenario is biased toward smaller EYO (a Beta(1,2) scaled between -10 and 15) values and the other is biased toward larger EYO values (a Beta(2,1) distribution scaled between -10 and 15).
- C. Simulate varying drop-out rates. A scenario with an annual drop-out rate of 3% per year and a scenario with an annual drop-out rate of 10% per year.
- D. Simulate different variance-covariance assumptions. The following scenarios are simulated: (1) the correlation between each pairwise measure is 0.25; (2) the correlation between each pairwise measure is 0.50; (3) the endpoints are uncorrelated; (4) each standard deviation is increased by 25%; (5) each standard deviation is decreased by 25%.
- E. Rate of decline. Two variations on the assumed rates of decline are simulated. We assume a 10% slower rate of decline for all endpoints and then a scenario with 10% faster rate of decline for all endpoints. These rates are assumed across the entire range of EYO, multiply each alpha in [Table 13](#) by 0.90 or 1.10, for all arms and all OBS data.

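### The simulations behind the 95.9% power and the 0.981 threshold omit the 6-month visits that the primary model will use; the stated power is probably conservative, and the threshold is unconfirmed for the planned data

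*SAP*

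**What the plan says.** - **Power.** Section 5 reports that the MDPM with dynamic borrowing "led to approximately 95.9% power for a 30% effect size" and refers to Appendix VI.
- **Threshold.** Section 12.1.5: "The threshold of probability of superiority determined by the simulation is 0.981". Under its rule, one cut-off must hold the one-sided error at 2.5% or less in every null scenario, with a floor of 0.975. Section 8.2 sets the target: "Each drug is considered to have its individual 2.5% type I error rate".
- **Simulated data.** Appendix VI generates a four-component outcome at each visit and lists "Frequency of cognitive assessments: Every 12 months" among its base assumptions. The allocation is "53:17 per arm, for 53:53:34 for each arm and the pooled placebo". The 66 DIAN-OBS subjects get their own follow-up length and otherwise follow the same recipe as trial subjects.
- **Planned data.** Appendix III: "Per protocol, the first three endpoints were collected semi-annually, while MMSE is collected annually". In its numbering the first three are MEMUNITS, WAIS and ISLT. It also says the model is fitted at any visit with one or more of the tests. Section 12.1.6.5 repeats the schedule and adds: "The ISLT was administered to DIAN-OBS subjects only from 2017".
- **Scenarios.** A to H in Appendix VI vary entry EYO, dropout, covariance, rate of decline, dose effect, DIAN-OBS sample size, and drift between DIAN-OBS and the trial. None varies visit frequency or ISLT availability.

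**The concern.** Appendix VI presents its base case as the best estimate of each parameter and was updated with the actual accrual, but it keeps annual testing without calling that a simplification. The same annual line stands in Appendix V. It fits there, because Section 12.1.9.1 does not compute the composite at visits where only some components are scheduled. It does not fit the MDPM, which takes in the 6-month visits. A carry-over is a plausible explanation, though the SAP does not say so.

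Two figures depend on this. The power in Section 5 and Table 15 is the power of a sparser dataset than the one to be analysed. The 0.981 cut-off, which decides success for each drug, was calibrated on that sparser dataset. The balance between randomized and DIAN-OBS information, which governs how far borrowing influences the result, also differs from what was simulated.

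**Working it through.** **1. The SAP's own figures.** The 95.9% equals the base entry of Table 15 at CPR 0.70 (0.959). The largest of the 13 null percentiles in Table 16 is 0.9801 (slower decline), consistent with a cut-off of 0.981. The two figures agree with their tables; the question is what data the tables describe.

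**2. SE implied by Table 15.** With power = Φ(−ln CPR / SE − z(0.981)), the implied SE is −ln CPR / (z(0.981) + z(power)), where z(0.981) = 2.075.
- CPR 0.70: 0.3567 / (2.075 + 1.739) = 0.0935.
- CPR 0.80: 0.2231 / (2.075 + 0.418) = 0.0895.

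**3. Effect of the 6-month visits on the SE.** The Bayesian simulation cannot be repeated from the text, so two approximations were used, both with the Table 13 curves, the stated residual covariance, accrual and 7% annual dropout.

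*(a) Decline curve treated as known, no borrowing.* Information on log CPR per subject, annual versus actual schedule: 8.82 vs 13.72 (CPR 1), 6.36 vs 8.97 (0.80), 4.47 vs 6.60 (0.70). SE = √[1/(53·I_active) + 1/(34·I_placebo)].
- CPR 0.80: 0.0794 falls to 0.0652, ratio 0.82.
- CPR 0.70: 0.0869 falls to 0.0707, ratio 0.81.

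*(b) Decline curve estimated, 66 DIAN-OBS subjects, borrowing SD τ fixed from 0.007 (near full) to 30 (none).*

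| CPR | τ | SE, annual | SE, actual schedule | Ratio |
|---|---|---|---|---|
| 0.80 | 0.007 | 0.0653 | 0.0529 | 0.81 |
| 0.80 | 30 | 0.0857 | 0.0675 | 0.79 |
| 0.70 | 0.007 | 0.0719 | 0.0577 | 0.80 |
| 0.70 | 30 | 0.0895 | 0.0705 | 0.79 |

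With MMSE rescaled (factor 0.43), the CPR 0.70, τ = 30 ratio is 0.0705/0.0902 = 0.78. Assumptions: other drug at CPR 1; ISLT at EYO +13 read as −2.95 (the printed −2.295 breaks the decline); monotonicity approximated by a random-walk prior; onset shift linearised.

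Neither approximation reproduces the SAP's power. For the annual design, (b) gives 0.968-0.997 at CPR 0.70 and 0.70-0.91 at CPR 0.80, both optimistic. Only the SE ratios are carried forward.

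**4. Effect of DIAN-OBS ISLT.** Removing all ISLT from DIAN-OBS, the extreme case, raises the SE by 0.2-1.1% (for example 0.0653 to 0.0660 at CPR 0.80, τ = 0.007).

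**5. Power with the ratios applied to the implied SEs.**

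| Change | SE ratio | CPR 0.70 (stated 0.959) | CPR 0.80 (stated 0.662) |
|---|---|---|---|
| No DIAN-OBS ISLT, annual visits | 1.011 | 0.955 | 0.652 |
| Actual visit schedule | 0.78 to 0.81 | 0.998 to 0.996 | 0.869 to 0.842 |
| Both, less favourable ratios of (b) | 0.81 × 1.011 = 0.819 | 0.995 | 0.834 |

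**6. Threshold.** It cannot be recomputed without the model code. Table 16 gives weak hints only. Decreased SD has 0.9653, base 0.9678, increased SD 0.9734; DIAN-OBS N = 120 has 0.9599 against 0.9678 for 66. Each row rests on 1,000 trials, so the Monte Carlo SE of a 2.5% tail is √(0.025 × 0.975 / 1000) = 0.0049. From the base row the local density is about (0.025 − 0.013)/(0.981 − 0.9678) = 0.91. The SE of a percentile is then about 0.005, and of a difference about 0.008. The gaps from base for the SD rows (0.0025 and 0.0056) and for N = 120 (0.0079) are no larger than that.

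**The case against.** The strongest reply is that no harm is shown. The stated power errs on the safe side, enrolment is complete, and 95.9% no longer drives a sample-size decision. All 13 null scenarios give a type I error between 0.009 and 0.023 at 0.981. Appendix VI also plans 10,000 permutations of the treatment codes on the real data, which carry the real schedule and the real ISLT gaps. Section 12.1.6.5 already plans one analysis without ISLT and one restricted to MMSE visits in the trial.

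Much of this stands. But the Section 12.1.6.5 analyses test the trial result, not the power or the cut-off. The permutation reports an error rate after the trial and states that no threshold will be adjusted. Neither supplies a threshold derived for the planned data.

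A reader might go further and infer that the simulations describe another design, or that 0.981 fails to control type I error. The documents support neither. Arms, allocation, accrual, follow-up and model match the plan; the one clear difference is visit density. No calculation here shows an error rate above 2.5%. That DIAN-OBS ISLT is complete in the simulation is itself an inference from the instruction to simulate the remaining components as for trial subjects; the SAP does not state it.

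**Conclusion.** The mismatch in visit schedule is explicit, and no scenario covers it. The SE of the treatment contrast under the planned schedule is about 18-22% below that of the simulated one. Power is therefore about 0.995 rather than 0.959 at CPR 0.70, and about 0.83 rather than 0.662 at CPR 0.80. The stated power is probably conservative, with the larger discrepancy at the smaller effect. These sizes assume independent residuals six months apart, as the MDPM itself does; autocorrelation between visits would shrink the gain. The DIAN-OBS ISLT gap is inferred and minor. Whether 0.981 is too high, right or too low for the planned data is unknown: it has not been shown to fail, and it has not been derived for those data.

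**What to change.** Before unblinding, re-run the Appendix VI null and power scenarios with MEMUNITS, WAIS and ISLT every 6 months, MMSE every 12 months, and DIAN-OBS ISLT present only where it was actually collected. Restate the Section 5 power and Tables 15 and 16. Then confirm 0.981, or replace it by applying the existing rule in Section 12.1.5 with its 0.975 floor. The cost is simulation time and replacement of these figures; nothing in the conduct of the trial changes.

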12.1.3 Primary Analysis of DIAN-MCE

The following analyses will be conducted for the mITT population and the eligible DIAN-OBS subjects.

A multivariate disease progression model (MDPM) with EYO time scale and a proportional treatment effect will be used to assess statistical differences in the rate of cognitive decline as measured by the four cognitive tests of DIAN-MCE simultaneously between each study drug arm, the mutation positive placebo arms (direct and concurrently randomized placebo subjects) and the eligible DIAN-OBS arm with dynamic borrowing in a single run (henceforth referred to as the 4-arm MDPM). The implementation of dynamic borrowing is presented in SAP [Section 12.1.4](#). The details of the MDPM are presented in SAP [Appendix III](#). Let the CPR denote the ratio of the rate of cognitive decline of one arm to the rate of cognitive decline of another arm. The MDPM will directly estimate three CPRs simultaneously. One is the ratio of the mutation positive placebo arm (post-baseline) to the eligible DIAN-OBS arm plus the baseline DIAN-TU-001 measurements (denoted as e^{θ_2}); the second is the gantenerumab active drug arm to the eligible DIAN-OBS arm (denoted as e^{θ_3}); and the third one is the solanezumab active drug arm to the eligible DIAN-OBS arm (denoted as e^{θ_4}). The treatment effect for each arm is reported compared to the mutation positive placebo arm. The treatment effect for gantenerumab is calculated using the posterior samples as $e^{\theta_3 - \theta_2}$ (or equivalently $\frac{e^{\theta_3}}{e^{\theta_2}}$), and for solanezumab as $e^{\theta_4 - \theta_2}$ (or equivalently $\frac{e^{\theta_4}}{e^{\theta_2}}$). The CPR that represents the treatment effect for each of the active drug arms ($\frac{e^{\theta_3}}{e^{\theta_2}}$ for gantenerumab and $\frac{e^{\theta_4}}{e^{\theta_2}}$ for solanezumab) will be relative to the mutation positive placebo.

The model behavior, the details for determining the threshold to control the type I error rate, and the estimated power are presented in SAP [Appendix VI](#).

The primary analysis for each study drug is testing the hypothesis that:

$$H_0: CPR \geq 1,$$

$$H_1: CPR < 1.$$

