- F. Dosing effects. Each patient underwent a dosing change in the trial. The effects for the active arms are assumed to potentially change upon dosing. The treatment effect parameter is assumed for the high dose. The relative effect of the low dose to the high dose is varied. The default assumptions above have the low dose effect equal to the high dose effect. Proportions of 0.75, 0.50, 0.25, and 0 are simulated. The timing of the dose change is assumed to be after 3 years for the first 14 subjects, after 2 years for the next 111 subjects, and after 1 year for the last 16 subjects.
- G. Differing DIAN-OBS sample size. Sample size of 120 is simulated. The inclusion of run-in data from the DIAN-OBS data may be more equivalent to 120 DIAN-OBS data being “borrowed.”
- H. Simulate variation between the DIAN-OBS data and the randomized arms. In each of these scenarios, all randomized arms are simulated as having proportional changes from the DIAN-OBS data. Proportional effects of 0.80, 0.90, 1.10, and 1.20 are assumed.

In each case, within each scenario we simulate 1000 trials. Each MCMC simulates 20,000 draws from the MCMC algorithm, with a burn-in of 5000 to calculate posterior probabilities. Each trial simulates the final analysis when the last patient reaches 4 years. The power values for all the scenarios are presented in [Table 15](#).

Table 15: Power for Each Study Drug Arm for Various Treatment Effect Sizes and Assumptions

Treatment Arm CPR*	A	B		C		D				
	Base	Larger EYO	Smaller EYO	Drop Outs 3%	Drop Outs 10%	0.25 Correlation	0.5 Correlation	0 Correlation	Increased SD 25%	Decreased SD 25%
1	0.013	0.015	0.016	0.016	0.015	0.016	0.012	0.010	0.017	0.010
0.80	0.662	0.843	0.406	0.746	0.632	0.654	0.653	0.794	0.539	0.880
0.75	0.861	0.965	0.589	0.907	0.837	0.845	0.831	0.927	0.717	0.978
0.70	0.959	0.993	0.764	0.981	0.930	0.946	0.936	0.982	0.857	0.996
0.65	0.983	0.998	0.896	0.993	0.982	0.983	0.979	0.993	0.960	1
0.60	0.996	0.998	0.949	0.997	0.997	0.998	0.995	0.998	0.986	1

*Treatment effect is the reduction in cognitive progression as measured by the (1-CPR) relative to the blinded placebo arm

Treatment Arm CPR*	E		F				G
	Slower Decline	Faster Decline	Low = 0.75	Low = 0.50	Low = 0.25	Low = 0	OBS N = 120
1	0.023	0.011	0.013				0.009
0.80	0.673	0.727	0.622	0.551	0.488	0.338	0.706
0.75	0.831	0.909	0.816	0.745	0.679	0.514	0.889
0.70	0.935	0.981	0.934	0.872	0.822	0.669	0.960
0.65	0.984	0.997	0.979	0.950	0.906	0.816	0.990
0.60	0.992	1	0.997	0.980	0.951	0.907	0.994

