This 97.5th percentile for each of these 13 scenarios (and combinations) is presented in [Table 16](#). The simulated type I error rate, using a probability of superiority threshold of 0.981, is reported in the last column.

Table 16: The 97.5th Percentile of the Posterior Probability of Superiority for the Null Hypothesis Scenarios. Using these as the threshold in that scenario would create a type I error rate of 2.5%.

	Simulation Scenario	97.5 th Percentile	Type I Error [contact]
A	Base	0.9678	0.013
B	Larger EYO	0.9713	0.015
	Smaller EYO	0.9723	0.016
C	2.5% Annual Drop-Out	0.9628	0.016
	10% Annual Drop-Out	0.9664	0.015
D	Correlation 0.25	0.9683	0.016
	Correlation 0.50	0.9669	0.012
	Correlation 0	0.9589	0.010
	Increased SD	0.9734	0.017
	Decreased SD	0.9653	0.010
E	Slower Decline	0.9801	0.023
	Faster Decline	0.9632	0.011
F	OBS N = 120	0.9599	0.009
Combined Nulls		0.9684	0.014

Post-Trial Permutation of Type I Error Rate

To justify that the model behaves similarly for the simulated data and for the actual patient data and to further verify the type I error rate, we will perform a null hypothesis permutation with the complete trial data. The details of this planned post-trial simulation are presented below. This post-trial simulation will be included in the CSR as supportive analyses for type I error control and a pure frequentist analysis of the Bayesian analysis. We permute the treatment assignment for randomized patients 10,000 times and calculate the frequency of these permutations that achieve the success threshold for the posterior probability and the frequency of permuted trials that achieve

the observed posterior probability for each arm as a permutation p -value. The permuted treatment assignments are all considered “null” scenarios.

- Using all the randomized subjects, a random permutation of the treatment code will be conducted. This will permute the treatment code of the 140 randomized patients. The primary analysis (4-arm MDPM; including the DIAN-OBS data) will then be applied to each of the 10,000 permuted datasets to estimate the CPR and posterior probability of superiority.
- The frequency of 10,000 permuted trials in which the posterior probability of superiority is greater than the pre-determined threshold will be reported and labeled as the “post-trial simulated type I error” of the trial. No pre-trial thresholds will be adjusted.

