- The frequency of the 10,000 permuted trials in which the posterior probability of superiority is greater than the actual posterior probability for each arm will be recorded and labeled as the permutation test p -values for each arm.

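### The post-trial permutation is a null only if neither drug has any effect, so its share above 0.981 is not the trial's type I error and each drug's p-value depends on the other drug

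*SAP*

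**What the plan says.** Section 12.1.3 sets a separate hypothesis for each drug, CPR >= 1 against CPR < 1, relative to placebo: "The treatment effect for each arm is reported compared to the mutation positive placebo arm".

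The last part of Appendix VI describes the permutation. On what is shuffled: "This will permute the treatment code of the 140 randomized patients". On what is refitted: "The primary analysis (4-arm MDPM; including the DIAN-OBS data) will then be applied to each of the 10,000 permuted datasets". On status: "The permuted treatment assignments are all considered" null scenarios. Two outputs follow. The share of permuted trials above the pre-set threshold is labelled the post-trial simulated type I error. Each drug's permutation p-value is the frequency of "permuted trials in which the posterior probability of superiority is greater than the actual posterior probability for each arm". On use: "This post-trial simulation will be included in the CSR as supportive analyses for type I error control", and as a purely frequentist reading of the Bayesian analysis. No threshold is changed by the result.

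The Type I Error Rate text of the same appendix takes the opposite view of one setting. It declines to count randomized effects of 0.70, 0.80 or 0.90 relative to DIAN-OBS as mathematical nulls, because the observational data enter the analysis. It calls these scenarios G. In the scenario list they are H, where "all randomized arms are simulated as having proportional changes from the DIAN-OBS data".

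**The concern.** The hypothesis concerns one drug against placebo. Shuffling three arms together generates a different situation, in which both drugs and placebo all decline at the average rate of the randomized cohort. In the planned 53:53:34 allocation, 106 of 140 subjects are on active drug. If the drugs work, every shuffled arm, including the shuffled placebo, declines more slowly than DIAN-OBS. The borrowing prior then pulls the shuffled placebo back towards DIAN-OBS, and the shuffled active arms look superior. This is the setting that Appendix VI itself says is not a null.

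The clinical study report could then show a large type I error and a weak permutation p-value beside a true positive. In the other direction, if one drug speeds decline, its subjects worsen the reference distribution for the other drug, and an inert partner gets too small a p-value.

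**Working it through.** **Inputs.** Allocation 53:53:34, 66 DIAN-OBS subjects in the base case, and threshold 0.981 (normal quantile 2.075), all from Appendix VI. Power values come from Table 15, columns A and H. The SAP gives no operating characteristics for the permutation itself.

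**1. Strength of borrowing, from Table 15 alone.** At CPR 0.80, power rises from 0.662 (base) to 0.981 when all randomized arms run at 0.80 of the DIAN-OBS rate. On the normal scale that is 2.075 - 0.418 = 1.66. The base null rate is 0.013 (quantile -2.226). Adding the shift gives -2.226 + 1.66 = -0.57, or about 28%. So a cohort at 0.80 of the DIAN-OBS rate, with no difference between its arms, would pass 0.981 about 28% of the time. Table 15 H has no CPR 1 row, so the SAP does not show this.

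**2. Approximation.** On log CPR, with r the randomized-to-DIAN-OBS rate, c the treatment CPR and w the weight of placebo in the borrowed control:

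Power = Phi((-ln(rc) + w ln r)/SE - 2.075)

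Fitting two parameters to 21 cells of columns A and H gives w = 0.327 and SE = 0.0900. DIAN-OBS then counts as 34 x 0.673/0.327 = 70 subjects (SAP: 66). Reproduction of the plan's figures:

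- Base: 0.657 at CPR 0.80 (SAP 0.662), 0.869 at 0.75 (0.861), 0.971 at 0.70 (0.959), and null 0.019 (0.013).
- H at CPR 0.80: 0.169, 0.379, 0.884, 0.981 (SAP 0.171, 0.407, 0.893, 0.981).
- 16 of 21 cells lie within 2 points; the largest error is 3.3 points.

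**3. Hand check of the share above 0.981.** After shuffling, c = 1 and ln r is the cohort mean log effect.

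- Both drugs at 0.70: (106/140) x ln 0.70 = -0.270. Then 0.673 x 0.270/0.0900 = 2.02, and Phi(2.02 - 2.075) = 48%.
- Both at 0.80: (106/140) x ln 0.80 = -0.169. Then 0.673 x 0.169/0.0900 = 1.26, and Phi(1.26 - 2.075) = 21%.

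**4. Simulation** of subject-level effects with all codes permuted (500 trials x 400 permutations; Monte Carlo error at most about 2.2 points):

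| CPR tested drug, other drug | Share of permutations above 0.981 | Permutation p <= 0.025 | Threshold rule |
|---|---|---|---|
| 1, 1 | 1.8% | 3.0% | 2.6% |
| 0.80, 0.80 | 21% | 33% | 66% |
| 0.75, 0.75 | 33% | 49% | 88% |
| 0.70, 0.70 | 48% | 66% | 98% |
| 0.80, 1 | 8% | 60% | 66% |
| 0.70, 1 | 15% | 96% | 97% |
| 1, 1.2 | 0.4% | 8% | 1.6% |
| 1, 1.3 | 0.3% | 13% | 1.6% |

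**5. Sensitivity to the borrowing model.** A fixed 63% pull towards DIAN-OBS (posterior SD 0.0905) gives shares of 17%, 28% and 42% with both drugs at 0.80, 0.75 and 0.70. Versions in which tau squared is estimated borrow less. They give 13-26%, losses of 19-34 points, and over-rejection of 6% at CPR 1.2 and 11-12% at 1.3. They fit Table 15 H less well: one returns 0.798 where the SAP has 0.981. With no borrowing, all three effects vanish.

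**6. Permuting one drug with placebo only.** Rejection for an inert drug is 3.0% and 2.0% when the partner has CPR 1.2 and 1.3. With both drugs at 0.70, the p-value reaches 0.025 in 85% of trials instead of 66%. The share above 0.981 is still 15% and 32% with both drugs at 0.80 and 0.70, so that share is not a type I error under this scheme either.

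**The case against.** The scheme is valid under the global null: with both drugs inert, rejection is near nominal. It also does something useful there. With inert drugs and a cohort at 0.80 of the DIAN-OBS rate, the actual false-positive rate in the approximation is about 28-33%, and the all-arm shuffle reports about 29-30%. It therefore exposes a danger that Table 16 leaves out. This stands, and is a reason to keep the shuffle under a correct label.

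The analysis is also supportive and changes no threshold. That stands too.

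A reader might infer that the trial's type I error is about 40%, or that the trial loses about 30 points of power. The documents support neither. The first would be a mislabelled output, and a value near 40% needs both drugs at about CPR 0.70 with strong borrowing. The second concerns only the supportive p-value; in the same simulation the primary rule still succeeds in 98% of trials.

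Finally, the figures rest on a normal approximation. With both drugs at 0.70 the shuffled cohort lies at about 0.76-0.77 of the DIAN-OBS rate, outside the 0.80-1.20 range of scenario H. The direction is secure; the exact size is not.

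**Conclusion.** The point holds in conditional form. Calling every permuted dataset null is right only if neither drug has any effect, and it conflicts with the appendix's own exclusion of randomized arms slower than DIAN-OBS. Each drug's p-value tests equality of all three arms, not that drug's hypothesis in Section 12.1.3.

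Size, over the variants tried:

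- Both drugs at CPR 0.80 to 0.70: reported type I error roughly 13-48%; permutation p-value 19-39 points less powerful than the primary rule.
- One drug working: about 8-15%, and a loss of 1-6 points.
- One drug at CPR 1.2 to 1.3 and the other inert: p <= 0.025 for the inert drug in about 6-13% of trials.

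These values assume borrowing of about the strength seen in Table 15 H and a placebo arm that declines as DIAN-OBS does. The SAP does not state the parametrization of its Inverse-Gamma prior. A reading with no borrowing would remove the problem, but Table 15 H rules that reading out for the simulated model. The primary decision is unaffected, so this should be corrected but does not invalidate the primary analysis.

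**What to change.** In Appendix VI:

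1. For each drug's permutation p-value, permute only that drug's active codes and the mutation positive placebo codes, and hold the other drug's codes as observed.
2. Delete the statement that all permuted assignments are null. Keep the all-arm shuffle, but report its share above 0.981 as a rejection rate under the global null only, not as the trial's type I error when either drug shows an effect.
3. Do not replace the shuffle with a simulation at the posterior mean of the borrowed theta2. That estimate is already shrunk to DIAN-OBS: with inert drugs and a cohort at 0.80 of the DIAN-OBS rate, it would report about 5% where the actual rate is about 28-33%. If a model-based check is added, take theta2 from the no-borrowing fit already planned in Section 12.1.6.4.

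The cost is wording, computing time, and about 10 points of power for the supportive p-value when only one drug works (about 85% against 95% at CPR 0.70). With both drugs at 0.70, the restricted p-value still falls about 12 points short of the primary rule.
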